| ICF | Informed Consent Form |
| ICSR | Individual Case Safety Report |
| IDMC | Independent Data Monitoring Committee |
| IMP | Investigational Medicinal Product |
| INR | International Normalised Ratio |
| | |

CLASP

| IRAS | Integrated Research Application System |
|----------|---|
| ISF | Investigator Site File |
| ISRCTN | International Standard Randomised Controlled Trials Number |
| IUD | Intrauterine device |
| IUS | Intrauterine hormone-releasing system |
| IV | Intravenous |
| IVOS(T) | Intravenous-to-oral switch (therapy) |
| MHRA | Medicines and Healthcare products Regulatory Agency |
| mRS | Modified Rankin Scale |
| NHS GG&C | National Health Service Greater Glasgow and Clyde |
| NICE | National Institute for Health and Care Excellence |
| NIHR HTA | National Institute for Health and Care Research Health Technology Assessment |
| NIHSS | National Institutes of Health Stroke Scale |
| NIMP | Non-Investigational Medicinal Product |
| ONS | Office for National Statistics |
| OR | Odds ratio |
| PI | Principal Investigator |
| PIS | Participant Information Sheet |
| PPIE | Patient and Public Involvement and Engagement |
| PROBE | Prospective, Randomised Open-label Blinded-Endpoint |
| PROMs | Patient-reported outcome measures |
| PSP | Post-Stroke Pneumonia |
| PV | Pharmacovigilance |
| QALYs | Quality-adjusted life years |
| R&I | Research & Innovation |
| RCB | Robertson Centre for Biostatistics |
| RCT | Randomised Controlled Trial |
| REC | Research Ethics Committee |
| RR | Respiratory Rate |
| RSI | Reference Safety Information |
| SAE | Serious Adverse Event |
| SAP | Statistical Analysis Plan |
| SAR | Serious Adverse Reaction |
| SDV | Source Data Verification |
| | |

IRAS 1009744

CLASP

| SIS | Stroke Impact Scale |
|-------|---|
| SIV | Site Initiation Visit |
| SOP | Standard Operating Procedure |
| SmPC | Summary of Product Characteristics |
| SSNAP | Sentinel Stroke National Audit Programme |
| SUSAR | Suspected Unexpected Serious Adverse Reaction |
| SViR | Stroke Voices in Research |
| TMG | Trial Management Group |
| TSC | Trial Steering Committee |
| UKCRC | UK Clinical Research Collaboration |
| VAP | Ventilator associated pneumonia |
| WBC | White Blood Cell |

iii. TRIAL SUMMARY

| Trial Title | CLArithromycin for post-Stroke Pneumonia: A prospective, randomised open-label blinded-endpoint phase 3 multicentre trial | | |
|------------------------------------|--|---|--|
| Internal ref. no. (or short title) | CLASP | CLASP | |
| Clinical Phase | Phase III | | |
| Trial Design | Prospective, randomised open (PROBE) | -label blinded-endpoint | |
| Trial Participants | People with Post-Stroke Pneur | monia (PSP) | |
| Planned Sample Size | 1166 | | |
| Treatment duration | 5 days | | |
| Follow up duration | 90 days (+/-7 for local research central follow-up) | n staff follow-up, +/-14 for | |
| Planned Trial Period | 60 months | | |
| | Objectives | Outcome Measures | |
| Primary | Determine whether 5 days of treatment with clarithromycin in addition to usual non- macrolide antibiotic treatment for PSP improves functional outcome at 90 days | Blinded modified Rankin Scale (mRS) at 90 days | |
| Secondary | Determine whether clarithromycin in addition to usual non-macrolide antibiotic treatment for PSP: | | |
| | Reduces mortality at 90 days | All-cause mortality at 90 days | |
| | Increases home time by 90 days | Days spent in pre-admission usual place of residence at 90 days | |
| | Reduces cardiovascular mortality at 90 days | Cardiovascular mortality at 90 days | |
| | Reduces urgent or unplanned readmissions at 90 days | Non-elective admissions by 90 days | |
| | Reduces recurrent stroke at 90 days | Stroke at 90 days | |
| | Reduces major cardiovascular events at 90 days | Major cardiovascular events at 90 days | |
| | Improves quality of life at 90 days | EQ-5D-5L at 90 days | |
| | Improves stroke-related health status at 90 days | Stroke Impact Scale (SIS) at 90 days | |
| | Reduces caregiver burden at 90 days | Zarit Caregiver Burden (ZBI- 12) interview | |

| | Is safe | Clostridioides difficile infection within 90 days Ventricular arrhythmia within 7 days |
|--|--|--|
| | Is cost-effective from the perspective of NHS England | Health and social care resource use up to 90 days |
| Investigational Medicinal Product(s) | Clarithromycin | |
| Formulation, Dose, Route of Administration | Clarithromycin 500 mg 12 hourly for 5 days, via IV or oral/enteral route as appropriate and in accordance with local IVOS policy | |

iv. FUNDING AND SUPPORT IN KIND

| FUNDER(S) | FINANCIAL AND NON-FINANCIAL SUPPORT |
|--|-------------------------------------|
| (Names and contact details of ALL organisations providing funding and/or support in kind for this trial) | GIVEN |
| National Institute for Health and Care Research (NIHR) Health Technology Assessment (HTA) | £3,238,557.07 |

This project is funded by the NIHR HTA programme (NIHR158678). The views expressed are those of the author(s) and not necessarily those of the NIHR or the Department of Health and Social Care.

v. ROLE OF TRIAL SPONSOR

Prior to study initiation, a non-commercially funded clinical trial co-sponsorship agreement will be put in place between NHS Greater Glasgow and Clyde (NHS GG&C) and the University of Glasgow. The roles and liabilities each organisation will take under the Medicines for Human Use (Clinical Trials) Regulations, 2004 SI 2001:1031 are laid out in this agreement signed by both organisations.

The University of Glasgow shall be responsible for carrying out the obligations and responsibilities set out in the aforementioned agreement and shall be deemed "sponsor" for the purposes of Part 3 of the regulations in relation to the study.

NHS Greater Glasgow and Clyde shall be responsible for carrying out the responsibilities set out in the agreement, and shall be deemed "sponsor" for the purposes of Parts 4, 5, 6, and 7 of the regulations in relation to the study.

The Co-Sponsors will delegate specific roles to the Chief Investigator (CI), Glasgow Clinical Trials Unit (GCTU) and other third parties. These arrangements will be clearly documented in agreements and/or the Sponsor Delegated Roles and Responsibilities Matrix.

vi. ROLES AND RESPONSIBILITIES OF TRIAL MANAGEMENT COMMITEES/GROUPS & INDIVIDUALS

The overall delivery of the trial according to the scientific protocol, budget and time will be the responsibility of the Chief Investigator and communicated directly through regular written reports to the funder.

Trial Management Group (TMG)

The trial will be coordinated from the University of Glasgow and NHS GG&C by the CLASP Trial Management Group (TMG). The TMG includes those individuals responsible for the day-to-day management of the trial: the CI and Co-CI, trial managers and representatives from GCTU, NHS GG&C and the University of Glasgow. The role of the group is to monitor all aspects of the conduct and progress of the trial, ensure that the protocol is adhered to and take appropriate action to safeguard participants and the quality of the trial itself.

Trial Steering Committee (TSC)

The role of the Trial Steering Committee (TSC) is to provide overall supervision of the trial and ensure that it is being conducted in accordance with the principles of Good Clinical Practice (GCP) and the relevant regulations. The TSC should:

- Agree the trial protocol and any substantial amendments
- Provide advice to the investigators on all aspects of the trial
- Have members who are independent of the investigators, in particular an independent Chair, aligned with NIHR recommendations
- Have a formal Charter outlining the roles and responsibilities of its members.

Decisions about continuation or termination of the trial or substantial amendments to the protocol are usually the responsibility of the TSC who will advise the Co-Sponsors.

The TSC will meet at the start of the study and regularly thereafter. The Committee may invite other attendees from the trial team to present or participate in discussions on particular topics. These attendees will be non-voting members.

Independent Data Monitoring Committee (IDMC)

The role of the Independent Data Monitoring Committee (IDMC) is to review the accruing trial data and to assess whether there are any safety issues that should be brought to participants' attention or any reasons for the trial not to continue. The IDMC will:

- Be independent of the investigators, the funder and Co-Sponsors
- Make recommendations to the TSC and Co-Sponsors
- Receive unblinded reports on study safety data, progress and outcomes
- Have a formal Charter outlining the roles and responsibilities of its members.

The IDMC will meet at the start of the study and at least annually thereafter.

vii. PROTOCOL CONTRIBUTORS

The protocol has been developed by a group with extensive clinical and research experience relevant to this study including the design and conduct of landmark trials. This includes specialists in stroke ([name], [name]), microbiology ([name]), respiratory and critical care ([name]), pharmacy ([name]), clinical trial design and biostatistics ([name]) and health economics ([name]).

[figure not shown]
Patient and Public Involvement and Engagement (PPIE) Group

A dedicated stroke survivor PPIE Lead and the Stroke Association's Stroke Voices in Research (SViR) Group were consulted to ensure that the trial design includes the priorities and views of stroke survivors. Key contributions to the trial design and delivery have included the appropriateness of the intervention and randomisation, eligibility criteria, approach to consent, outcome measures, widening participation, diversity and inclusion, 90-day follow-up processes and dissemination of findings to participants and their families. The PPIE Group is led by [name].

viii. KEY WORDS:

Stroke, Post-Stroke Pneumonia, Cerebrovascular, Antibiotics, Macrolide, Clarithromycin, Microbiology

ix. TRIAL FLOW CHART

1 BACKGROUND

Stroke is a leading cause of death and disability worldwide. In the UK, there are around 100,000 new strokes each year [1]. Pneumonia (an infection in the lungs), is a serious complication of stroke which occurs most often in the first week after stroke onset and contributes significantly to worse clinical outcomes and healthcare costs. Overall, pneumonia occurs in around 14% of stroke admissions [2,3,4].

Post-Stroke Pneumonia (PSP), is considered a separate entity to pneumonia in other clinical settings, such as community-acquired pneumonia (CAP), hospital acquired pneumonia (HAP) or ventilator associated pneumonia (VAP), due to the specific clinical context [2,5]. Increasing age, worse stroke severity and swallowing impairment (dysphagia) are consistent risk factors for development of PSP [6]. Acute stroke also induces both activation and suppression of systemic inflammatory and immune responses [7], and a localised inflammatory response in the lungs [8,9]. It is thought that aspiration of naso-pharyngeal and oro-gastric material due to dysphagia, plus exposure to healthcare-associated bacteria, in the setting of impaired systemic innate and adaptive immunity are the key aetiological processes in PSP. PSP is associated most often with organisms seen in HAP, predominantly Gramnegative bacteria (e.g. Klebsiella pneumoniae, Escherichia coli, Pseudomonas aeruginosa) and Staphylococcus aureus. Streptococcus pneumoniae, a common cause of CAP, is identified infrequently in PSP (around 3.5%) [5]. Pulmonary inflammation in acute stroke is characterised by perivascular and peribronchial inflammation, with increased numbers of pulmonary neutrophils and plasma cells, and increased pro-inflammatory cytokine concentrations, which are augmented in the presence of pneumonia [8.9]. Systemic inflammation induced by stroke, for example measured by elevated plasma interleukin-6 or C-reactive protein (CRP) concentration, is enhanced in PSP and contributes to worse clinical outcomes [10].

PSP has a profound impact on people with stroke, their families and stroke services. In a recent study of UK stroke units in the Sentinel Stroke National Audit Programme (SSNAP), we found that inhospital mortality in people with pneumonia occurring within 7 days of admission was 40% compared to 13% in those without pneumonia occurring within 7 days of admission (Figure 1) [4]. Patients with early PSP had an increased risk of longer length of hospital stay, increased odds of worse functional outcome at discharge and increased risk of in hospital mortality, despite adjustment for prognostic variables and modern stroke unit care (Table 1) [4]. In another UK study, PSP was associated with increased acute care costs and resulted in an adjusted incremental cost of £5817 (95% Confidence Interval £4945, £66890) per patient [11]. Furthermore, patients with post-stroke infections are also at an increased risk of any unscheduled re-admission, recurrent ischaemic stroke and post-stroke cognitive decline [12,13,14].

[figure not shown]

Figure 1: Stacked bar chart showing distribution of scores on the modified Rankin Scale (mRS) for patients with early PSP and those without early PSP. mRS of 6=died

| Length of hospital stay, adjusted IRR (95% CI) | 1.27 (1.25, 1.30) |
|--|-------------------|
| mRS at discharge, adjusted OR (95% CI) | 2.9 (2.9, 3.0) |
| In-hospital mortality, adjusted HR (95% CI) | 1.78 (1.74, 1.82) |

Table 1: Association between PSP and outcomes adjusted for prognostic variables and markers of good quality stroke unit care. IRR = incidence rate ratio. OR = odds ratio. HR = hazard ratio.

There are very limited strategies to prevent occurrence of PSP and trials of prophylactic antibiotics have failed to prevent PSP or improve clinical outcomes (see systematic search and individual participant data analysis [15]). Pneumonia as a complication of stroke is a top-10 research priority identified by the Stroke Association/James Lind Alliance priority setting partnership [16]. The importance of PSP has been recognised by the initiation of a European Stroke Organisation (ESO) guideline group to deliver best practice recommendations for clinical care.

2 RATIONALE

Antibiotics are the mainstay of treatment for PSP, however there is a lack of evidence to guide treatment compared to other types of pneumonia as identified in our recent systematic review [17], for example CAP [18]. The effectiveness of different antibiotic classes and the importance of potential immunomodulatory effect of some drug classes in PSP remains uncertain. This trial is a pragmatic randomised trial of immunomodulatory macrolide antibiotic therapy added to usual, non-macrolide antibiotic treatment for PSP, which could improve clinical outcomes for patients and their families and provide health economic benefits. Our results will directly inform national stroke treatment guidelines and clinical practice.

Macrolide antibiotics have powerful immunomodulatory properties and have been shown to reduce exacerbations in people with chronic obstructive pulmonary disease (COPD) and to improve lung function in people with cystic fibrosis [19]. Given the clear role of inflammation in PSP, macrolides are logical agents to assess to see whether their antimicrobial and immunomodulatory effects improve the poor outcomes in PSP. Whilst there may be differences in immunomodulatory effects between macrolide drugs, immunomodulation is generally accepted to be a class effect [20]. There is no

consistent difference in side effect profile between different macrolides [21]. Of the newer macrolides, clarithromycin and azithromycin are available as oral or intravenous (IV) formulations. In our recent survey of UK stroke units, IV and oral clarithromycin were available in 93% of responding units, whereas IV azithromycin was only available in 45% of units. This is important as the majority of patients with PSP have dysphagia and require IV antibiotics, at least until a consistent oral or enteral route is established. We have therefore chosen clarithromycin for this trial. We have opted for 5 days treatment with clarithromycin to align with current antibiotic recommendations for pneumonia and to reduce the risks of antimicrobial resistance [18,22]. Given their poor outcome, the presence of a usually severe stroke and possible dysphagia, participants would be considered seriously ill and requiring initial intravenous therapy (dose 500 mg twice daily). As soon as a reliable oral or enteral route is established, participants should switch to oral/enteral dosing at the dose for severe respiratory infection (500mg twice daily) in line with usual IVOS policies.

2.1 Assessment and management of risk

We have identified the following main areas of risk:

- Adverse reactions and drug interactions from clarithromycin use
- Potential risk from combination antibiotic therapy
- Inclusion of women of childbearing potential
- Changes to antibiotic therapy during the treatment phase of the study
- Potential risk of unblinding of outcome assessors

2.1.1 Potential for adverse reactions and drug interactions and mitigation of this risk

The most frequent adverse reactions of macrolides are gastrointestinal disturbances such as abdominal pain, diarrhoea, nausea and vomiting and taste disturbance. When given intravenously, injection site phlebitis and pain can also occur.

There is a risk of QT prolongation and ventricular arrhythmia when clarithromycin is used concomitantly with medicines such as domperidone and ivabridine in people with a history of QT prolongation or ventricular arrhythmia and in people with uncorrected hypokalaemia or hypomagnesaemia. There is an increased risk of myopathy and rhabdomyolysis when clarithromycin is used concomitantly with HMG-CoA reductase inhibitors (statins) that are extensively metabolised by CYP3A4 (including lovastatin, simvastatin and atorvastatin).

The SmPC advises caution in people with coronary artery disease, bradycardia and severe cardiac insufficiency. Participants will be randomised in acute stroke services and will be under regular monitoring as part of routine clinical care so people with these conditions can be included if they meet all other eligibility criteria.

The potential risks associated with clarithromycin will be minimised by avoiding use in people who are known to be intolerant (included as a trial exclusion criteria) and avoiding concomitant use with medicines which have known interactions or increase risk of QT prolongation. Concomitant use of medicines that are listed as contraindicated in the SmPC or as 'manufacturer advises avoid' in the BNF will not be permitted unless these can safely be stopped or temporarily withheld for the duration of clarithromycin treatment plus 3 days (72 hours) to allow >5 half-lives to elapse. In addition, we have excluded additional medications which could be associated with adverse reactions that could be difficult to detect or where clarithromycin levels could be significantly reduced. These are listed in Appendix 2. In addition, medications that can interact with clarithromycin but can be used with caution are listed in Appendix 3. The use of anticoagulant drugs is allowed after consideration of the risks and benefits. There is emerging evidence that DOACs pose little risk of bleeding complications in the early period after ischemic stroke and would not normally be use in people with intracerebral haemorrhage. Stroke physicians are well experienced in assessing these relative risks and benefits. The use of

calcium channel blockers, digoxin and drugs for diabetes mellitus is allowed as these can be readily monitored in routine practice and stroke physicians are experienced with these drugs. Corticosteroids, cilostazol and omeprazole use is allowed as the potential for significant adverse effects is low with a short duration of treatment. Omeprazole and cilostazol can usually be withheld for a short period or alternative agents can be used.

In addition, risk is mitigated by the fact participants will be randomised and initially treated in acute stroke services and by avoiding clarithromycin use in the following people:

- People with QT prolongation
- People with a history of long QT syndrome or ventricular arrhythmia or cardiac arrest.

People with these features will also be excluded from the trial. Hypokalaemia and hypomagnaesemia are also risk factors for QT prolongation. People with known hypokalaemia (defined as K+ < 3.5 mmol/l) or known hypomagnaesemia (defined as Mg2+ < 0.70 mmol/l) at the point of screening will be excluded from the trial. They can later be included if this is corrected and they remain eligible. People with hypokalaemia or hypomagnesaemia prior to screening that has already been corrected can also be included.

Clarithromycin is routinely used in clinical practice and information on clinically relevant interactions and contra-indications is well documented and easily accessible (e.g. SmPC and BNF), further minimising potential risks.

Clostridioides difficile infection is a documented risk from use of antibiotic therapy. There is uncertainty regarding any excess risk from clarithromycin use. An evidence summary published by NICE in 2015 [23] found that macrolides are likely to be associated with an increased risk of *C.difficile* infection but this risk is equivalent to use of penicillins and is likely less than antibiotics such as clindamycin, cephalosporins and tetracyclines [24].

Statins will be frequently used in this population. People prescribed statins can be randomised but suspension of statin therapy whilst receiving clarithromycin is required by the protocol [25]. There is no RCT evidence to support use of statins earlier than 7 days after stroke onset [26] and no evidence that delaying statin use for a short period will be detrimental.

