6.2 Exclusion criteria

- Requirement for macrolide therapy as usual care
- Confirmed respiratory viral infection (e.g. COVID-19, influenza) at point of screening*
- Known antibiotic treatment for chest infection or pneumonia within the last two weeks (single doses or less than 3 days of treatment is allowed)
- Known toxin positive *C.difficile* infection in the past 12 weeks
- Contraindications or major cautions to macrolide antibiotic use:
 - Known hypersensitivity to clarithromycin, its excipients or other macrolide antibiotics
 - Established diagnosis of myasthenia gravis
 - Diagnosis of long QT syndrome
 - QTc interval >460ms on last ECG before screening[†][36]
 - Known hypokalaemia (K+ < 3.5 mmol/l) which has not been corrected

- Known hypomagnesaemia (Mg2+ < 0.70 mmol/l) which has not been corrected
- History of ventricular tachycardia
- History of cardiac arrest
- Severe hepatic impairment defined as AST, ALT or bilirubin > 3 times ULN or known diagnosis of cirrhosis
- Current use of medicine(s) known to increase risk of QT prolongation that in the opinion of the investigator cannot reasonably be withheld for the duration of study treatment plus 3 days (see Appendix 2)
- Current use of medicine(s) that are contra-indicated in combination with clarithromycin that in the opinion of the investigator cannot reasonably be withheld for the duration of study treatment plus 3 days (see Appendix 2)
- Women of childbearing potential who are pregnant, breastfeeding or who are unwilling to use appropriate contraception or abstain from sexual intercourse for 3 days (72 hours) after the last dose of clarithromycin (see Appendix 1 for definitions and information on acceptable methods of contraception)
- Plan for imminent mechanical ventilation
- End-of-life care
- Previously randomised into the CLASP study

* A test for viral infection is not required by protocol, this is only if it is done for routine clinical care.

[†]Some ECG machines may provide different measures of QTc. For trial eligibility, the longer result should be used.

Co-enrolment in other Clinical Trial of Investigational Medicinal Products (CTIMPs) is not permitted while participating in CLASP. Co-enrolment in observational studies, diagnostic studies or other research may be permitted subject to agreement of the Sponsors and Chief Investigators of both studies.

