7.9 Withdrawal criteria

7.9.1 Withdrawal from clarithromycin treatment (intervention arm)

Participants may be withdrawn from the study treatment by local clinical teams in the event of a Serious Adverse Reaction (SAR) and it is felt that it is in the best interest of the patient to discontinue treatment. Participants allocated to the intervention arm will also be withdrawn from clarithromycin treatment in the event:

- Treatment is initiated with a prohibited medicine, where the prohibited medicine has not been temporarily discontinued by the local PI (see Appendix 2)
- Requirement for macrolide therapy as part of evolving antibiotic use
- Known toxin positive *C.difficile* infection
- The participant deteriorates after enrolment and becomes for palliative care only
- Onset of contraindications or major cautions to macrolide antibiotic use:
 - Hypersensitivity to clarithromycin, its excipients or other macrolide antibiotics
 - Diagnosis of long QT syndrome
 - Any event of QTc prolongation of >20ms compared to the baseline value
 - Ventricular tachycardia
 - Cardiac arrest
 - Any occurrence of severe hepatic impairment defined as AST, ALT or bilirubin >3 times ULN

Discontinuation of treatment by local clinical teams does not require withdrawal of the participant from the study and follow-up can be continued.

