8.8 Known drug reactions and interaction with other therapies

Clarithromycin is a widely used macrolide antibiotic, with a known potent inhibitory effect on CYP34A. Drugs that are primarily metabolised by CYP34A may have elevated and prolonged therapeutic concentrations when administered concomitantly with clarithromycin and are prohibited. Conversely, drugs which are potent inducers of CYP3A may lower the plasma levels of clarithromycin and are

therefore also prohibited. The most likely relevant drug interactions in this population are use of statins and ticagrelor. However, a participant may still be enrolled if, in the local investigator's opinion and judgement, the prohibited medication can be temporarily stopped during the duration of the clarithromycin treatment (see section 8.9 below).

For detailed information on drug-drug interactions, please refer to the relevant SmPC or other local prescribing resources. Prohibited concomitant medicines are provided in Appendix 2. Please note this list is not exhaustive. Medicines with a known interaction which may be co-administered at investigator's discretion are provided in Appendix 3. See also information on permitted dose modifications in section 8.7.

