8.9 Concomitant medication

A participant's concomitant medication should be checked by a medically qualified investigator before randomisation to ensure eligibility and to ensure appropriate action is taken regarding concomitant medication.

Participants prescribed or taking prohibited medicines as listed in Appendix 2 are ineligible for the study unless in the investigator's opinion the interacting medicine can safely and appropriately be withheld for the duration of clarithromycin treatment plus 3 days. Should an indication for these drugs develop during the study treatment period and treatment with a prohibited medicine commence, participants must be withdrawn from study clarithromycin treatment. Participants will also permanently stop trial clarithromycin treatment should clarithromycin (or other macrolide) become clinically indicated for antibiotic treatment as per local antimicrobial policies. Relevant data should continue to be collected on participants providing consent is still in place.

Participants prescribed or taking medication listed in Appendix 3 can be enrolled in the study at investigator discretion following consideration of advice contained in the protocol, the BNF and the SmPC.

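### Sections 2.1.1 (statin paragraph) and 8.8 leave out the further 3 days of withholding that sections 2.1.1, 6.2 and 8.9 require for prohibited drugs (minor)

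*Protocol*

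**What the plan says.** Three places give the longer period.

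- Section 2.1.1 does not permit use of contraindicated drugs alongside clarithromycin unless they can be stopped or "temporarily withheld for the duration of clarithromycin treatment plus 3 days (72 hours) to allow >5 half-lives to elapse".
- Section 6.2 excludes patients on QT-prolonging or contraindicated medicines that, in the investigator's opinion, "cannot reasonably be withheld for the duration of study treatment plus 3 days (see Appendix 2").
- Section 8.9 makes patients on Appendix 2 drugs ineligible unless the drug "can safely and appropriately be withheld for the duration of clarithromycin treatment plus 3 days".

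Appendix 2 lists ticagrelor and, for this study, all statins.

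Two places give a shorter period.

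- The statin paragraph later in section 2.1.1 says that patients on statins can be randomised but "suspension of statin therapy whilst receiving clarithromycin is required by the protocol".
- Section 8.8 states that "The most likely relevant drug interactions in this population are use of statins and ticagrelor", and then allows enrolment if, in the local investigator's judgement, "the prohibited medication can be temporarily stopped during the duration of the clarithromycin treatment (see section 8.9 below").

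**The concern.** The same drugs are covered by two periods that do not match, and section 8.8 names those drugs as the likeliest interactions. Section 2.1.1 also expects statins to be in frequent use. It gives the reason for the 72 hours (more than five half-lives) and names the hazard: myopathy and rhabdomyolysis with statins that depend heavily on CYP3A4, such as simvastatin and atorvastatin.

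Two things are at stake. The first is safety: someone who reads only the statin paragraph or section 8.8 could take the obligation to end with the last clarithromycin dose. The second is eligibility: a patient whose ticagrelor can be paused for the treatment course, but not for 3 days more, passes on the words of section 8.8 taken alone and is excluded by section 6.2. Section 13.5 allows no eligibility waivers, so the two sections should not differ.

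**Working it through.** No sample size, power or error-rate figure is involved. The check is a comparison of texts and a subtraction.

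**Inputs**

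- Treatment length: 10 doses at 12-hour intervals over 5 days (section 8.6).
- Longest dosing window if doses are missed: 7 days (section 8.6).
- Added withholding time: 3 days, stated as 72 hours (section 2.1.1). Check: 3 × 24 = 72 hours.

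**Comparison**

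| Place | Form of the statement | Period |
|---|---|---|
| 2.1.1, interactions paragraph | Condition for permitting use | Treatment + 72 h |
| 6.2 | Exclusion criterion | Treatment + 72 h |
| 8.9 | Condition for eligibility | Treatment + 72 h |
| 2.1.1, statin paragraph | Description of a requirement | Treatment + 0 h |
| 8.8 | Condition for enrolment, with a pointer to 8.9 | Treatment + 0 h |

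**Size of the gap**

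- Nominal course: 5 + 3 = 8 days against 5 days. Difference: 3 days = 72 hours.
- Longest dosing window: 7 + 3 = 10 days against 7 days. Difference: 3 days = 72 hours.

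The difference does not depend on how treatment is counted.

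**Is there a statin exception that would reconcile the two?** No. Appendix 2 brings all statins under the general rule, and no section sets a shorter period for them. The two short statements are omissions, not a separate rule.

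**Does any of the five statements give a restart time?** Not in so many words. The three longer ones imply it, but they are framed as whether the drug can be withheld. The consequences attached to starting a prohibited drug concern stopping clarithromycin. Section 8.9 applies to the treatment period ("Should an indication for these drugs develop during the study treatment period and treatment with a prohibited medicine commence"), and section 7.9.1 lists as a ground for withdrawal from clarithromycin "Treatment is initiated with a prohibited medicine, where the prohibited medicine has not been temporarily discontinued by the local PI". A plain restart sentence would therefore add something.

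**The case against.** The strongest reply is that the protocol already has the rule right where it counts. The exclusion criteria and the concomitant medication section agree with each other. Section 8.8 sends the reader to 8.9. The statin paragraph is a short remark in the risk rationale, and the 72-hour rule with its half-life reason stands earlier in the same section. Section 8.9 also has a medically qualified investigator check concomitant medication before randomisation. All of this stands, and it limits the point to a minor one.

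Three stronger readings are tempting, and the documents do not support them.

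- *A reader might infer that the short statements are the operative instruction after the last dose.* They are not. Section 8.8 is itself an enrolment condition, of the same kind as 8.9. Neither short statement speaks about the time after the last dose. The general rule in section 2.1.1 is a limit on permitted use and already carries the 72 hours.
- *A reader might infer that restart falls to untrained ward staff.* The statement in section 8.6 that clinical staff need no study-specific training concerns changes to clarithromycin dose and route, not the restarting of Appendix 2 drugs. That section also keeps investigator oversight and provides a Clinical Information Sheet, whose content is not shown.
- *A reader might express the gap as a share of the withholding period lost.* Any such share assumes a restart at the last dose, which no section tells sites to do.

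The reply does not remove the difference itself. Two sections still state a shorter period, and the one in the statin paragraph carries no pointer to 8.9.

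**Conclusion.** The inconsistency is real and minor. Two statements of a safety and eligibility rule fall 72 hours short of the other three, for the drugs that the protocol considers most likely to matter. The intended rule is clear: treatment plus 3 days.

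The conclusion rests on the wording alone. It assumes nothing about how many participants take these drugs or how many sites would misread the text, since the protocol gives neither figure. Harm would require a site to rely on the short wording and restart early. Section 2.1.1 itself reports no evidence that a short delay in statin use is detrimental, so it gives no reason to hurry. Sample size, error rates and the primary analysis are not affected.

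**What to change.** 1. In the statin paragraph of section 2.1.1 and in section 8.8, state the period as: during clarithromycin treatment and for 3 days (72 hours) after the last dose.
2. Add one sentence to section 8.9: Appendix 2 drugs stopped for the trial must not be restarted until 72 hours after the last clarithromycin dose.

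The cost is a phrase in two places and one new sentence, through the usual amendment process. No visit, test, data item or participant is added. A site that had followed the shorter wording would withhold these drugs 3 days longer, which section 8.9 already requires the investigator to judge safe and appropriate for a patient on such a drug to be eligible.
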